21.1 Schedule of Events and Assessments (Continued)

	Screening Period	Double-blind Treatment Period								Safety Follow-up Period	
		Day -1 (Dosing and Postdose)	Day 1 (Time 0)	Day 2	Day 3	Day 4 (EOT/ET)	Unscheduled Visit ^m	Clinic visit	Telephone call		
Visit Day	-28 to -2	Day -1 Predose							7 days after EOT	30 days after last dose	
Visit window (# days)		0	0	0	0	0	0		±3	+4	
Global evaluation of study drug				X	X	X	X				
C-SSRS	X	X					X				
PK blood sample collection ⁱ		X		X	X	X					
Issue diary							X ^l				
Collect diary									X		
Prior and concomitant medications	X	X	X	X	X	X	X	X	X	X	
Assessment of adverse events	X	X	X	X	X	X	X	X	X	X	

AE=adverse event; COVID-19=Coronavirus disease 2019; C-SSRS=Columbia-Suicide Severity Rating Scale;

ECG=electrocardiogram; EOT=end of treatment; ET=early termination; SAE=serious adverse event

a Vital signs will be evaluated starting at Screening; Day -1 predose and on Day 1 every 2 hours for the first 6 hours after the initial dose. Vital signs then to be evaluated every 6 hours thereafter until Day 4/end of treatment. A 15-minute window is permitted for vital sign measurements.

b Height and BMI will only be measured and calculated at the Screening visit; weight will be measured at Screening and Day -1 predose.

c A single 12-lead ECG will be performed at Screening, on Day -1 predose, on Days 1 through 3 at 1 hour postdose (the first dose of the day), and EOT/ET. A 1-hour window is permitted for the predose ECG and a 20-minute window is permitted for the postdose ECGs.

d Applicable to women of childbearing potential. A serum pregnancy test should be performed at Screening and a urine test must be performed at clinic check-in, prior to surgery.

e COVID-19 diagnostic polymerase chain reaction (PCR) test at Screening and a rapid antigen test on Day -1 predose.

f Subjects will be trained on the process for completion of pain assessments.

g Block Quality assessments are to be performed and recorded hourly (±15 minutes) on Day -1 until the block is removed, except between 2200 and 0600 hours when the subject is asleep. Between these hours, the subject will not be awoken, except at 0300 hours (±15 minutes) when the assessment is to be completed.

h Subjects should not have ice administered to the surgical area within the 30 minutes prior to each pain assessment. Pain (efficacy) assessments are to be recorded hourly (±15 minutes) for a 12 hour interval on Day 1 beginning immediately prior to the fifth dose (time 0) administered in the study. Pain assessments will continue every 3 hours during the subsequent 12 hour interval, and then every 6 hours thereafter until 72 hours, then once daily in the morning until the follow-up clinic visit. Rescue medication use is to be recorded until the safety follow-up clinic visit. Pain intensity should also be obtained immediately prior to rescue medication being taken.

i Record name, amount, date, and time of rescue medication ingested and current pain score until the follow-up clinic visit 7 days after EOT.

j PK blood samples will be collected Day -1 (predose, within one hour of dosing), Day 1 (one sample taken between 2-3 hours and one sample taken between 4-6 hours, after the first dose of the day), Day 2 (prior to the first dose of the day), and Day 3 (one sample taken between 2-6 hours and one sample taken between 8-12 hours, after the first dose of the day); and in the event of an SAE or an AE leading to discontinuation. A 15-minute window is permitted around each nominal timepoint on Day 1 and beyond.

k The physical exam on Day 4 (EOT/ET) must include an exam of the operative site. The physical exam at the follow-up visit 7 (± 3) days after the EOT procedures is for examination of the operative site only. Examination of the operative site must include visual inspection.

l Diary will be issued to take home which will be returned at the follow-up clinic visit 7 days after EOT.

m The designated study procedures are to be completed; however, the Investigator may complete any study procedure deemed necessary.

21.2 Multiple Imputation Details

The multiple imputation will be performed in a multi-step process:

1. Subjects with missing Time 0 assessments will be imputed by using the mean of the non-missing Time 0 assessments of the same treatment group.
2. Subjects that take rescue medications within 4 hours prior to a scheduled assessment will have the scheduled value replaced with the pre-rescue value for the purposes of imputation. If the scheduled value is higher than the pre-rescue value, it will not be replaced.
3. The dataset will be transposed to create a one-observation-per-patient dataset with variables representing the values at each scheduled time point (T_0 T_1 T_2 T_3 T_4 T_5 T_6 T_7 T_8 T_9 T_10 T_11 T_12 T_15 T_18 T_21 T_24 T_30 T_36 T_42 T_48 T_54 T_60 T_66 T_72). Site indicator variables (with values 0/1) will be created for the sites (with one less variable than number of sites). For the purposes of illustration, the follow text assumes 4 sites and three variables (S_1 S_2 S_3).
4. Values will be imputed assuming missing at random to create 50 complete datasets with values for all time points.
5. Subjects that drop out for adverse events or lack of efficacy will have their post-dropout missing values reset to missing.
6. Subjects with nonmissing values at 1 hour (aka T_1 variable) will have the T_1 variable replaced with $\max(T_0, T_1)$; this will include ALL subjects that do not drop out due to AE or lack of efficacy (LOE) (thus, may include values imputed in prior steps) and subjects that drop out due to AE or LOE prior to them dropping out. Proc MI will then be run including the site variables (S_1 S_2 S_3) and the two NRS variables through 1 hour: (T_0, T_1).
7. Subjects that had non-missing T_1 will have their values returned to their prior state (NOT the max of T_0, T_1), and the process will be repeated for T_2: Patients with

nonmissing values at 2 hours (aka T_2 variable) will have the T_2 variable replaced with max(T_0, T_1, T_2); this will include ALL subjects that do not drop out due to AE or LOE (thus, may include values imputed in prior steps) and subjects that drop out due to AE or LOE prior to them dropping out. Proc MI will then be run including the site variables (S_1 S_2 S_3) and the three NRS variables through 2 hours: (T_0, T_1, T_2).

8. This will be repeated iteratively up to the 72-h time point, building up to a complete dataset. This exercise yields values that are based on the distribution of the worse values through the time point being imputed for dropouts due to AE/LOE.
9. This complete dataset will be used ONLY to fill in monotone missing values starting at subject dropout. No observed values from the original dataset will be replaced and intermittent missing values and values following rescue med administration will be handled as described in above in the [Section 5.2.1](#) when calculating AUCs. This will result in 50 records for each patient for each AUC_{0-time}.

The following sample code represents the imputation in step 4 above:

```
proc mi data=nr0 seed=7238364 n impute=50 out=nr0 minimum=xx maximum=xx;  
mcmc impute=full chain=multiple;  
by TRT01P;  
var S_1 S_2 S_3 T_0 T_1 T_2 T_3 T_4 T_5 T_6 T_7 T_8 T_9 T_10 T_11 T_12 T_15  
T_18 T_21 T_24 T_30 T_36 T_42 T_48 T_54 T_60 T_66 T_72;  
run;
```

The following sample code represents the imputation in step 6 above:

```
proc mi data=nr0 seed=7238364 + seq# n impute=1 out=nr1 minimum=xx maximum=xx;  
mcmc impute=full chain=multiple;  
by imputation TRT01P;  
var S_1 S_2 S_3 T_0 T_1;  
run;
```

The following sample code represents the imputation in step 7 above:

```
proc mi data=nr1 seed=7238364 + seq# n impute=1 out=nr2 minimum=xx maximum=xx;  
mcmc impute=full chain=multiple;  
by imputation TRT01P;  
var S_1 S_2 S_3 T_0 T_1 T_2;  
run;
```

The following list of seeds will be used when needed for MI procedures or other analyses call for a random number seed. Each will only be used once, but if additional seeds are required, they will be chosen by adding one to a digit from the below list in an organized manner. For example, the primary analysis may use the list in order as it appears; a sensitivity may add one to the final digit of each; a second sensitivity may add one to the first digit of each. The actual seeds used will be captured in the analysis dataset programing specifications.

Seed 7238364 will be used for the multiple imputation other than placebo-based approach.
Seed 1592743 will be used for the placebo based multiple imputation.

Replace Steps 6-8 with the following sample code to achieve control-based copy-placebo imputation for missing data due to AE and LOE:

```
PROC MI DATA=MONO SEED=xxxxxx NIMPUTE=1 OUT=OUTM1 minimum=xx maximum=xx;
  CLASS TRT01PN;
  BY _IMPUTATION_;
  VAR S_1 S_2 S_3 AVAL1 AVAL2 AVAL3.....;
  MONOTONE REG (AVAL2 AVAL3.....);
  MNAR MODEL (AVAL1 AVAL2 AVAL3...../ MODELOBS = (TRT01PN = '1')) ;
RUN;
```

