 - Multiple imputation will be used to impute values at the scheduled assessment times for subjects that discontinue. For the purposes of imputation, unscheduled values and pre-rescue values will not be included, but will be added back into the dataset prior to calculating the AUC; however, scheduled values will be replaced with pre-rescue values during the censoring period prior to the imputation (and solely for the purpose of imputation). First, subjects that discontinue for reasons other than lack of efficacy (LOE) and

adverse events (AEs) will have their values imputed within treatment group with MI assuming MAR with covariates for all observed time points. For subjects who discontinue due to AEs or LOE, the MI will be based off the distribution of worst values through the time of discontinuation. This will be done iteratively for each time point starting at the earliest time point with missing data; covariates will be included for observed data through that time point. Full details of the MI algorithm are given in [Appendix 21.2](#).

In general, the area under the curve (AUC) from start time of interest, t_{start} , to end time of interest, t_k , for each subject will be calculated using the linear trapezoidal method. All pain assessments (including unscheduled) will be used in the calculation.

$$AUC_{t_{start}-t_k} = \sum_{i=start}^{k-1} \frac{1}{2} * (Pain_i + Pain_{i+1}) * (t_{i+1} - t_i)$$

Where i indexes the timepoints from 0 hour to 72 hours as 0 to 24; $start$ is the index value of the starting time; k is the index value of the end time; t_{start} is the start time of the AUC to be calculated; t_k is the end time of the AUC to be calculated; $Pain_i$ is the NRS pain intensity score at index i ; t_i is the time at index i . **Note:** The index count will be adjusted on an individual basis to account for unscheduled assessments and pre-rescue assessments. Calculations will be performed at a 1-minute precision, but final values will be scaled to hours, thus the AUC_{0-24} will be scaled 0-240.

For the primary efficacy endpoint the formula would be as follows:

$$AUC_{0-24} = \sum_{i=0}^{16-1} \frac{1}{2} * (Pain_i + Pain_{i+1}) * (t_{i+1} - t_i)$$

Note: The index count will be adjusted to account for unscheduled assessments.

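### SAP Appendix 21.2, steps 6-8, feeds AE/LOE leavers' imputed maxima forward as ordinary scores, so their imputed pain drifts above the worst-value distribution it is meant to follow

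*SAP*

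**What the plan says.** SAP 5.2.1 (item 4) and Appendix 21.2 describe the primary handling of AE/LOE leavers. In step 6, every subject who has a 1-hour score has it overwritten by the larger of the 0- and 1-hour scores, and the leavers' missing 1-hour score is imputed from that. Step 7 opens: "Subjects that had non-missing T_1 will have their values returned to their prior state (NOT the max of T_0, T_1". For the 2-hour score, "Proc MI will then be run including the site variables (S_1 S_2 S_3) and the three NRS variables through 2 hours". The sample code for this step is "proc mi data=nr1 seed=7238364 + seq# n impute=1 out=nr2 minimum=xx maximum=xx", so it reads the output of step 6. Step 8: "This will be repeated iteratively up to the 72-h time point, building up to a complete dataset".

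Step 8 describes the result: "This exercise yields values that are based on the distribution of the worse values through the time point being imputed". Section 5.2.1 puts the target differently: "the MI will be based off the distribution of worst values through the time of discontinuation". On predictors it says: "covariates will be included for observed data through that time point". The estimand in 13.1.1 refers to the worst pain actually observed before the intercurrent event.

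**The concern.** The reset in step 7 covers only subjects who had a score. A leaver's column keeps its imputed maximum. At the next step the model is fitted to donors, with their maximum as outcome and raw earlier scores as predictors. It is then applied to a leaver whose earlier columns already hold maxima. The step from raw score to maximum is counted again each time, and no later step undoes it.

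The procedure feeds the primary AUC0-24 analysis and the other AUC endpoints, which are analysed the same way. The size of the drift depends on how many assessments are scheduled after exit, not on any assumption in the estimand. It raises the mean of whichever arm loses more subjects to AE or LOE. LOE exits on placebo would flatter the drug; AE exits on drug would penalise it.

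**Working it through.** **1. The plan's own figure (SAP 3.5).** Difference 23, SD 50, 76 per arm, two-sided 0.05.
- SE of the difference = 50 × √(2/76) = 8.11.
- 23/8.11 = 2.84, giving power of 80.9% by the normal approximation (80.4% by noncentral t). 76/0.95 = 80.
- The plan's figure is reproduced, and 8.11 serves as the yardstick below.

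**2. The recursion, for a leaver whose last score is at 4 h.** Write M_k for the maximum of T_0 to T_k.
- 5 h: donors' M_5 is regressed on raw T_0..T_4. The leaver's T_0..T_4 are also raw, so the draw is fair.
- Donors' T_5 goes back to raw; the leaver's T_5 column holds a draw of M_5.
- 6 h: donors' M_6 is regressed on raw T_0..T_5. If b is the coefficient on T_5, the leaver's prediction is raised by b × (M_5 − T_5) over what the fitted model means.
- 7 h: the T_5 and T_6 columns both hold maxima, and so on.

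There are 25 scheduled times, hence 16 steps to 24 h and 24 to 72 h. After exit at 4 h, 12 times remain to 24 h (5 to 12, 15, 18, 21, 24). Eleven of them use at least one imputed maximum as a predictor.

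**3. Size, by simulation of steps 6-8 on the SAP's time points.** None of these inputs is in the documents: mean NRS falling from 6 to 4.5, between-subject SD 2.0, within-subject SD 1.5, autocorrelation 0.6, site terms omitted, 20,000 subjects. The resulting AUC0-24 SD is 47.7, near the planned 50.

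| Leaver, limits | Quantity | True running maximum | As written | Excess |
|---|---|---|---|---|
| Unselected, exit 1 h, 0-10 | 2 h score | 6.67 | 6.60 | −0.07 |
| | 12 h score | 7.61 | 8.65 | +1.04 |
| | 24 h score | 7.72 | 8.89 | +1.17 |
| | AUC0-24 | 177.2 | 197.0 | +19.8 |
| Unselected, exit 8 h, 0-10 | AUC0-24 | 166.7 | 170.9 | +4.2 |
| High-pain, exit 4 h, 0-10 | AUC0-24 | 210.0 | 213.3 | +3.3 |
| High-pain, exit 4 h, none | AUC0-24 | 210.0 | 231.5 | +21.5 |

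The first imputed point shows no upward excess; the excess builds afterwards. That locates the fault in the recursion, not in the choice of a maximum as target. In 400 simulated arms of 80 with 4 leavers, leavers' mean AUC0-24 was 183.7 as written against 172.7, an excess of 11.0. Over the wider set of assumed variance structures the excess is roughly +6 to +25 for unselected leavers (earlier exit is worse) and about +1 to +11 for high-pain leavers.

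**4. Effect on the comparison.**
- If 4 of 80 (5%) in an arm leave this way, its mean rises by 0.05 × 6 = 0.3 to 0.05 × 25 = 1.25 points, about 0.3 to 1.2.
- If 8% leave in one arm and 2% in another, the difference shifts by 0.06 × 6 = 0.36 to 0.06 × 25 = 1.5 points. Divided by 8.11, that is 0.04 to 0.18 SE.

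**5. Planned sensitivity analyses.** In SAP 13.1.2.2, items 2 and 3 use the worst-value rule and inherit the recursion. Item 1 (missing at random) and item 4 (placebo-based, which replaces steps 6-8) avoid it. The rescue-window analyses in 13.1.2.1 keep the rest of the imputation unchanged, so they inherit it too.

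**The case against.** The strongest reply is that little turns on it. Subjects are inpatients with two levels of rescue (Protocol 3.1.2 and 4.8.1), exits after 24 h cannot touch the primary endpoint, and no AE/LOE exit rate is stated. The 5% in SAP 3.5 concerns exclusion from the analysis. A shift of 0.04 to 0.18 SE at an assumed 8% versus 2% split will rarely change a conclusion. That stands.

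LOE leavers are also likely to be in high pain, where the net excess is small; with stricter selection it can vanish. That stands in part. The scale limit produces it: without limits the same leavers overshoot by 21.5 points. The SAP leaves the limits as placeholders.

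Analyses 1 and 4 bypass the recursion. True, but they change the missing-data assumption as well, so a discrepancy could not be traced to this fault.

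Two stronger readings are tempting. One is that 5.2.1 already confines predictors to scores observed before exit. Its clause, "covariates will be included for observed data through that time point", follows a description of an iterative procedure and defers to the appendix for details. It says nothing of runs by exit time, so it does not settle the matter. The other is that the step 8 description is simply false. Step 8 says only that values are based on that distribution. Drift away from it is shown; a broken promise to reproduce it is not.

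**Conclusion.** The fault is real and can be read from the text and code: predictors and target are different quantities for donors and leavers, and the mismatch compounds. It is minor to moderate. The per-leaver excess in AUC0-24 is material, but its effect on an arm mean is about 0.3 to 1.2 points at an assumed 5% exit rate, against 23 planned. The sizes rest on assumed means, variances, exit times and limits of 0-10. The direction of the drift is firmer than its size.

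A reader might infer that the primary result is compromised, or tilted toward the drug. The documents support neither: they give no exit rate, the tilt depends on which arm loses more subjects, and equal losses partly cancel.

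**What to change.** Before unblinding, make predictors and target the same quantity in steps 6-8:

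- Build running-maximum columns M_0..M_k for all subjects: donors, and leavers up to exit.
- Impute a leaver's missing M_k in sequence from site and M_0..M_(k-1), and use it only to fill post-exit values. Never mix raw donor scores and imputed maxima in the T columns.
- Change the VAR lists to match, and make the same change in sensitivity analyses 2 and 3 and in the rescue-window analyses.
- State the minimum and maximum and how they are enforced. A bounded draw pulls near-ceiling leavers down, so no repair is exact for them.
- Reconcile the target. Section 5.2.1 stops at discontinuation, 13.1.1 uses pain observed before the event, and step 8 has "values that are based on the distribution of the worse values through the time point being imputed". The columns above serve the step 8 target; either of the others would need steps 6-8 rewritten differently.

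Imputing from pre-exit scores alone would also stop the recursion. However, it fell 4 to 12 points short of the running maximum for high-pain leavers and understated the AUC spread in most scenarios. Running-maximum columns did better overall and are as simple.

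The cost is SAP wording and code. No new data are needed. The endpoint is unchanged, and so is the estimand unless the reconciliation alters it.

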21.3 Summary of Version Changes

Version No:	Document History Description of Update	Author(s)	Version Date
1.0	Original Version	[REDACTED]	14 March 2022
